4.2. Number of Subjects

Approximately 200 subjects are planned to be enrolled in this study to meet the number of subjects required for assessment of the primary endpoint. The Sponsor will periodically monitor the rate of positive ¹⁸F-DCFPyL PET/CT scans and the number of evaluable subjects that contribute to the efficacy assessment. If the observed rate of positive ¹⁸F-DCFPyL PET/CT scans is lower than expected, the sample size may need to be increased. When the required number of subjects are evaluable for calculation of the primary endpoint, subject enrollment and follow-up assessments will conclude.

See [Section 5](#) for eligibility criteria and [Section 10.1](#) for complete sample size assumptions.

4.3. Study Procedures

See [Figure 1](#) for the study schema and [Table 3](#) Schedule of Assessments for a comprehensive summary.

4.3.1. Screening (Day -30 to 1)

The following screening procedures and assessments must be completed prior to ¹⁸F-DCFPyL dosing and PET/CT imaging (Day 1):

- Obtain informed consent

- Demographic information, including date of birth, race, ethnicity, height and weight
- Clinically relevant medical history
- Prostate cancer history, including disease history, staging, and treatment(s)
- Conventional imaging findings per institutional standard of care (SOC) scan(s) (e.g., pelvic CT/MRI, whole-body bone scan, NaF, fluciclovine or choline PET) completed within 60 days prior to Day 1. SOC scan(s) performed more than 60 days prior to Day 1 may be repeated as a study Screening procedure and reviewed by the investigator prior to Day 1.

Subjects who provide signed informed consent and meet all eligibility criteria during Screening must also complete the following additional procedures prior to ¹⁸F-DCFPyL dosing PET/CT imaging (Day 1):

- Obtain a blood draw for PSA (total) and send to the central lab. If done on Day 1, the blood draw should be collected prior to ¹⁸F-DCFPyL dosing.
- The treating investigator completes the Pre-PyL Medical Management Questionnaire (MMQ) to document the initial intended management plan for the subject based on available clinical information and local conventional imaging results.

4.3.2. ¹⁸F-DCFPyL – Dosing and PET/CT Imaging (Day 1)

Subjects will visit the clinic for ¹⁸F-DCFPyL dosing and whole-body PET/CT imaging on Day 1.

Prior to receiving ¹⁸F-DCFPyL Injection, perform the following:

- Measure vital signs (blood pressure and heart rate);
- Record current medications and procedures and note changes from Screening.

All subjects are to receive a prescribed dose of 9 mCi (333 MBq) ¹⁸F-DCFPyL Injection. Dosing adjustments of ¹⁸F-DCFPyL are not permitted. See [Section 7.6](#) Study Drug Administration for details.

After dosing of ¹⁸F-DCFPyL Injection and within approximately 60-120 minutes post-¹⁸F-DCFPyL dosing, perform the following:

- Measure vital signs (blood pressure and heart rate);
- Acquire a single PET/CT scan from mid-thigh to skull (See [Imaging Manual](#) for guidelines);
- Record treatment-emergent adverse events (AEs) and any new medications and/or procedures since prior to ¹⁸F-DCFPyL dosing.

The site's local interpretation of ¹⁸F-DCFPyL PET/CT results will be recorded in the eCRF. See the [Imaging Manual](#) for ¹⁸F-DCFPyL PET/CT interpretation guidelines.

4.3.3. Safety Follow-up (phone call; Day 8 [±3])

A safety phone call at 7 (±3) days post-¹⁸F-DCFPyL dosing is required for all subjects who received any dose of ¹⁸F-DCFPyL to capture any late-occurring AEs and concomitant

medications and procedures. If Efficacy follow-up occurs within 7 (\pm 3) days post-¹⁸F-DCFPyL dosing, the Safety phone call will not be completed, and the late-occurring AEs and concomitant medications and procedures will instead be collected at the time of the Efficacy follow-up.

See [Section 9](#) Assessment of Safety for complete details.

4.3.4. Post-PyL Intended Management Plan (Day 2-60)

For all subjects who complete the PyL PET/CT scan, the Post-PyL MMQ will be completed by the treating investigator based on the additional result from the local PyL PET/CT scan to document whether a change to the initial intended management plan may be warranted due to the PyL finding. The Post-PyL MMQ should be completed within 60 days following ¹⁸F-DCFPyL PET/CT imaging.

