3.2. Secondary Endpoints

3.2.1. Secondary Efficacy Endpoints

- The percentage of subjects with a change in intended prostate cancer treatment plans due to ¹⁸F-DCFPyL PET/CT as measured by comparison of intended management questionnaires completed Pre- and Post- ¹⁸F-DCFPyL PET/CT imaging results

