4. INVESTIGATIONAL PLAN

4.1. Overall Study Design

This is a phase 3, multi-center, open-label, single-arm, non-randomized study to evaluate the diagnostic performance and safety of ¹⁸F-DCFPyL (PyL) PET/CT in subjects with suspected recurrence of prostate cancer and negative or equivocal findings per institutional standard of care conventional imaging. This study is planned to be conducted in approximately 15 sites in the United States and Canada, and to be conducted in conformance with Good Clinical Practices (GCP).

Eligible subjects (see [Section 5](#) for Eligibility Criteria) will be enrolled in a non-randomized, sequential manner, with competitive enrollment between study sites. Enrolled subjects will receive a single dose of 9 mCi (333 MBq) ¹⁸F-DCFPyL Injection followed by a single PET/CT scan acquired at 1-2 hours post-dosing.

Only subjects with positive PyL PET/CT scans (detection of disease at any site) will be followed at the Efficacy visit(s) (See [Table 3](#) Schedule of Assessments). Subjects will undergo Efficacy follow-up based on their PyL PET/CT finding(s) per local interpretation and clinical presentation for evaluation of the composite truth standard as defined in [Section 8.1](#).

If biopsy or surgery of a lesion identified on PyL PET/CT is feasible, attempts will be made to obtain tissue corresponding to the PyL-suspected lesion(s) within 60 days following PyL PET/CT imaging. If local histopathology results are obtained, they will be recorded in the eCRF and if the results are evaluable for prostate cancer, the subject will complete the study.

If histopathology (from biopsy or surgery) is not evaluable, or biopsy or surgery of the PyL-suspected lesion was not performed, an attempt will be made to anatomically correlate the PyL-suspected lesion(s) with conventional imaging modality per the Investigator's discretion within 60 days following PyL PET/CT imaging. The conventional imaging scan will be sent to the central imaging core lab for review. If the scan is deemed evaluable by the central imaging core lab, the subject will complete the study.

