4.3.5.1. Verification of PyL-suspected lesion (per local PyL PET/CT finding)

Subjects with at least one positive lesion identified per local PyL PET/CT imaging will undergo Efficacy follow-up for the composite truth standard as defined in [Section 8.1](#). Concomitant medications and procedures will be collected at the time of the Efficacy follow-up visit(s). See [Table 3](#) Schedule of Assessments.

Biopsy or Surgery within 60 days following ¹⁸F-DCFPyL PET/CT

At least 12 hours from time of ¹⁸F-DCFPyL dosing and no more than 60 days following PyL PET/CT imaging (Day 1) and prior to initiation of any radiation or systemic therapies for prostate cancer, an image-guided biopsy or surgery (e.g. salvage pelvic lymph node dissection) of a lesion identified by PyL PET/CT scan is encouraged if clinically feasible.

For subjects undergoing image-guided needle biopsy, the needle biopsy images (e.g., CT, TRUS-MRI, US) of the procedure will be sent to the central imaging core lab.

Local histopathology results of tissue(s) obtained will be recorded in the eCRF. Subjects with an evaluable histopathology result for prostate cancer will have completed the study. If evaluable histopathology result is not available, then subjects will undergo conventional imaging follow-up within 60 days following ¹⁸F-DCFPyL PET/CT imaging. See [Section 8](#) Assessment of Efficacy.

Conventional imaging within 60 days following ¹⁸F-DCFPyL PET/CT

If biopsy or surgery is not clinically feasible on a lesion identified by PyL PET/CT scan, conventional imaging based on the Investigator's discretion (e.g., targeted MRI or CT; fluciclovine or choline PET) on the PyL-suspected lesion will be performed and sent to the central imaging core lab. The choice of the most appropriate conventional imaging modality will be at the discretion of the investigator; use of the most sensitive imaging method is encouraged, such as targeted MRI for verification of the PyL-suspected bone lesion(s).

Subjects with informative conventional imaging of the anatomical correlate to the PyL-suspected lesion(s) based on central imaging core lab review will have completed the study.

See [Section 8](#) Assessment of Efficacy.

Initiation of locoregional radiation therapy (RT) in subjects without evaluable histopathology result or informative conventional imaging of the PyL-suspected lesion(s) within 60 days following ¹⁸F-DCFPyL PET/CT

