If an evaluable histopathology result for prostate cancer is not available and follow-up conventional imaging of the PyL-suspected lesion is not informative, subjects initiated on locoregional RT alone (no concomitant ADT) within 60 days following PyL PET/CT imaging will be followed every 3 months (± 7 days) for up to an additional 9 months to assess PSA response to RT alone (without concomitant ADT administered during this time). To be evaluable for PSA response, applicable subjects should undergo RT with fields and target volumes adjusted based on presence of PyL-positive prostate bed, pelvic nodal, visceral or limited osseous metastases.

A blood draw for PSA (total) will be obtained and sent to the central lab at each follow-up assessment. PSA response is defined by decline of $\geq 50\%$ from baseline PSA and must be confirmed within 4 weeks. Subjects will complete follow-up within the 9-month duration once PSA response is confirmed per the central lab.

Concomitant medications and procedures will be collected. See [Section 8](#) Assessment of Efficacy.

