- Surgery or biopsy to occur at least 12 hours from time of ¹⁸F-DCFPyL dosing but not more than 60 days following ¹⁸F-DCFPyL PET/CT imaging. Imaging used to guide biopsy (e.g., CT, MRI-TRUS, US) will be submitted to the central core imaging lab.
- Follow-up conventional imaging (e.g., targeted MRI/CT, fluciclovine or choline PET) per Investigator's discretion of the anatomical correlate to the lesion(s) identified on ¹⁸F-DCFPyL PET/CT is required in subjects whom evaluable histopathology for prostate cancer is not available. The image(s) will be submitted to the central core imaging lab for review and determination of evaluability.
- If evaluable histopathology result for prostate cancer is not available and follow-up conventional imaging of the PyL-suspected lesion is not informative, subjects initiated on locoregional radiation therapy (RT) alone within 60 days following PyL PET/CT (with no concomitant ADT administered during this time) will be followed every 3 months (± 7 days), up to 9 months post-initiation of RT. PSA response (decline of ≥50% from baseline PSA) must be confirmed (two consecutive levels within 4 weeks) per central lab evaluation.
- Pre-PyL Medical Management Questionnaire (MMQ) will be completed by the treating investigator for all subjects enrolled (who signed informed consent and met all eligibility criteria) in the study prior to Day 1.
- Post-PyL MMQ will be completed by the treating investigator for all subjects who completed ¹⁸F-DCFPyL PET/CT imaging.

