5.1.2. Secondary Endpoints

The percentage of subjects with a change in intended prostate cancer treatment plans due to ¹⁸F-DCFPyL PET/CT as measured by comparison of intended management questionnaires completed Pre- and Post- ¹⁸F-DCFPyL PET/CT imaging results (based on local reader interpretation) (see Section 8.5.3).

The endpoint is the percentage of subjects with a change in intended prostate cancer treatment plan from Pre- and Post ¹⁸F-DCFPyL PET/CT scan assessed using the MMQ, based on local ¹⁸F-DCFPyL PET/CT scan read results, as the decision to change the subject's treatment plan or not to change plans is made using this data.

Any change in planned management, whether from no treatment to any treatment, from one treatment to another between treatment categories or within a treatment category will be tabulated as a change. Change vs. no change will be analyzed as a binary response.

The shifts between no planned treatment and the major categories of planned therapy as well as between those categories are defined in Table 5.

Table 5: Changes in Planned Therapy

Pre- ¹⁸ F-DCFPyL PET/CT scan	Post- ¹⁸ F-DCFPyL PET/CT scan
No treatment planned	Any treatment planned
Any treatment planned	No treatment planned
Treatment planned - local therapy	Treatment planned - systemic therapy
Treatment planned - systemic therapy	Treatment planned - local therapy
Treatment planned - local therapy	Treatment planned - other therapy
Treatment planned – systemic therapy	Treatment planned - other therapy
Treatment planned – other therapy	Treatment planned – systemic therapy
Treatment planned – other therapy	Treatment planned – local therapy

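### The Post-PyL management questionnaire may be completed at any time up to Day 60, with no rule placing it before follow-up results or treatment, so the secondary endpoint can mix PyL-driven plan changes with later ones

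*Protocol*

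**What the plan says.** Protocol 3.2.1 words the endpoint causally: "The percentage of subjects with a change in intended prostate cancer treatment plans due to" the PyL scan, from a comparison of the pre- and post-scan MMQs. Protocol 4.3.4 says that the treating investigator completes the second form on the basis of the local scan result, "to document whether a change to the initial intended management plan may be warranted due to the PyL finding". Its timing rule is "The Post-PyL MMQ should be completed within 60 days following" the scan. Table 3 places the form in the Day 2 to 60 efficacy follow-up column, and footnote 9 says only that the "Post-PyL MMQ will be completed by the treating investigator for all subjects who completed" imaging.

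Three other activities share that window:

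- Biopsy or surgery (Protocol 4.3.5.1) may begin 12 hours after the injection; its outer limit is "no more than 60 days following PyL PET/CT imaging (Day 1) and prior to initiation of any radiation or systemic therapies".
- Follow-up imaging (Protocol 4.1): where histopathology is absent or not evaluable, "an attempt will be made to anatomically correlate the PyL-suspected lesion(s) with conventional imaging modality per the Investigator's discretion within 60 days". Table 3 footnote 6 makes this imaging a requirement for those subjects.
- RT start (Protocol 4.3.5.1): the PSA-follow-up path covers "subjects initiated on locoregional RT alone (no concomitant ADT) within 60 days following PyL PET/CT imaging".

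SAP 5.1.2 gives the counting rule: "Any change in planned management, whether from no treatment to any treatment, from one treatment to another between treatment categories" or within one, is tabulated as a change. SAP 8.5.3 analyses change versus no change on the FAS with a two-sided 95% CI.

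**The concern.** The endpoint asks what the scan did to the plan, but the counting rule asks only whether the two forms differ. They agree when the second form is completed while the scan is the only new information. Once a biopsy report or follow-up MRI is in hand, a form recording the current plan reflects the scan and the work-up together.

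This can distort the estimate in two ways. A plan left alone after PyL but altered by the later result is counted as a PyL effect. A plan altered by PyL and then returned to its starting point by a negative result is counted as no change. This endpoint is the only efficacy measure of the first secondary objective, and its confidence interval would not reveal either error.

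**Working it through.** **1. Is an order set anywhere?** Other sequences are fixed. The Pre-PyL MMQ must precede dosing (Protocol 4.3.1, Table 3 footnote 8). Biopsy must precede radiation or systemic therapy (4.3.5.1). Truth-standard imaging must precede locoregional or systemic treatment (8.1). For the Post-PyL MMQ, Protocol 4.1, 4.3.4, 8.6 and Table 3 footnote 9 give its information basis or its window, but no order relative to the work-up. SAP Table 7 lists no MMQ window.

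**2. Is the investigator shielded from later results?** No. Histopathology is read locally (8.4), and Protocol 6.4 lets site staff use all local images and clinical information for management planning.

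**3. Would the analysis detect it?** SAP 5.1.2 and 8.5.3 contain no attribution rule, no check of form date against other dates, and no sensitivity analysis on timing.

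**4. Scale.** The documents give no expected value or null for this endpoint, so only planning figures are available. The stated sample size reproduces:

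- 1.96² × 0.3 × 0.7 / 0.10² = 80.67, rounded up to 81 positive scans.
- 80.67 / 0.60 = 134.5 (stated as 134).
- 134 / 0.70 = 191.4, rounded up to 192.

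I use N = 192 and the 60% positive rate from Protocol 10.1. The other rates are assumptions:

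- L = share of scan-positive subjects whose form follows a work-up result or treatment start.
- a = share of those whose recorded change came only from the later event.
- r = share of those whose PyL-driven change was reversed by it.

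Net shift = 0.60 × L × (a − r).

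| L | size of (a − r) | shift, points | subjects of 192 |
|---|---|---|---|
| 10% | 10% | 0.6 | 1.2 |
| 25% | 25% | 3.75 | 7.2 |
| 50% | 50% | 15.0 | 28.8 |

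The sign is that of (a − r), which the documents do not determine. For comparison, the 95% CI half-width is 1.96 × √(p(1−p)/192): 6.5 points at p = 30% or 70%, and 7.1 at 50%.

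**5. Would dropping out-of-order forms solve it?** Take assumed change rates of 70% in scan-positive and 30% in scan-negative subjects, with no contamination. The FAS rate is 0.6 × 0.7 + 0.4 × 0.3 = 54%. Drop half of the positives and it becomes (0.3 × 0.7 + 0.4 × 0.3) / 0.7 = 47%. Exclusion alone would move the estimate by about 7 points.

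**The case against.** The strongest reply is that the documents already fix what the form rests on. Protocol 4.1, 4.3.4 and 8.6 and SAP section 4 tie it to the added PyL result, and SAP 5.1.2 says that the decision is made using the local read. That stands as a statement of purpose, so contamination is permitted rather than instructed. It does not stop an investigator who holds a biopsy result from recording the current plan.

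Second, the work-up exists because the scan was positive, and the RT on the PSA path is to be shaped by PyL-positive sites (Protocol 4.3.5.1, 8.5). Some later changes are thus indirectly PyL effects. This also stands in part: the documents do not say whether such changes count, and a treatment start is not in itself contamination.

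Third, the MMQ form and eCRF pages are not among the documents. They may already hold a date or an attribution item, so their absence cannot be asserted.

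A reader might infer four stronger claims, none of which the documents support:

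- *The change rate is inflated.* A negative follow-up result can reverse a PyL-driven change and lower the rate.
- *A form completed on, say, Day 45 necessarily follows the work-up.* Biopsy and imaging may run to Day 60, and may be not performed or unevaluable.
- *Only scan-positive subjects are affected.* The planned work-up is confined to them, but scan-negative subjects have the same 60-day form window, in which other events can occur.
- *All positive subjects must start RT within 60 days.* That limit applies to the PSA-follow-up path.

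**Conclusion.** The concern holds as a gap in timing and attribution: the windows coincide, no order is set, and the SAP counts any difference for an endpoint defined by cause. The bias may run either way. Under the assumed rates it ranges from about one subject in 192 to twice the sampling half-width, and the documents do not narrow that range. It concerns one secondary proportion, for which no null value or success threshold is given, and leaves the primary CLR untouched. It is worth correcting because the correction is cheap.

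**What to change.** **Protocol 4.3.4, 8.6 and Table 3 footnote 9.** Require the Post-PyL MMQ after the local PyL report, before the investigator receives any follow-up biopsy, surgery or imaging result, and before new prostate cancer treatment starts. The rule governs the form only and does not alter the timing of care. Capture the completion date if the eCRF does not already do so.

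**SAP 8.5.3.** Keep the full FAS estimate as the main analysis. Add a sensitivity analysis by form timing relative to follow-up results and treatment start. For example, count out-of-order forms that record a change as no change; the mirror-image count (out-of-order forms with no recorded change counted as change) would cover reversals. Do not exclude out-of-order forms: that would selectively remove scan-positive subjects from an endpoint defined on all FAS subjects whatever their scan result. State whether changes reached through PyL-triggered work-up are meant to count.

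**Cost.** Wording in both documents, an earlier form deadline for investigators, and one more table. If the protocol can no longer be amended, the SAP analysis is still feasible wherever form, procedure and treatment dates are recorded.

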4.3.5. Efficacy Follow-up (Performed or Initiated by Day 2-60)

Only subjects with positive PyL PET/CT scans (detection of disease at any site) per local interpretation will continue to be followed for verification of PyL-suspected lesion. Subjects who do not have a positive PyL PET/CT result will have completed the study after completing the Safety follow-up.

4.3.5.1. Verification of PyL-suspected lesion (per local PyL PET/CT finding)

Subjects with at least one positive lesion identified per local PyL PET/CT imaging will undergo Efficacy follow-up for the composite truth standard as defined in [Section 8.1](#). Concomitant medications and procedures will be collected at the time of the Efficacy follow-up visit(s). See [Table 3](#) Schedule of Assessments.

Biopsy or Surgery within 60 days following ¹⁸F-DCFPyL PET/CT

At least 12 hours from time of ¹⁸F-DCFPyL dosing and no more than 60 days following PyL PET/CT imaging (Day 1) and prior to initiation of any radiation or systemic therapies for prostate cancer, an image-guided biopsy or surgery (e.g. salvage pelvic lymph node dissection) of a lesion identified by PyL PET/CT scan is encouraged if clinically feasible.

For subjects undergoing image-guided needle biopsy, the needle biopsy images (e.g., CT, TRUS-MRI, US) of the procedure will be sent to the central imaging core lab.

Local histopathology results of tissue(s) obtained will be recorded in the eCRF. Subjects with an evaluable histopathology result for prostate cancer will have completed the study. If evaluable histopathology result is not available, then subjects will undergo conventional imaging follow-up within 60 days following ¹⁸F-DCFPyL PET/CT imaging. See [Section 8](#) Assessment of Efficacy.

Conventional imaging within 60 days following ¹⁸F-DCFPyL PET/CT

If biopsy or surgery is not clinically feasible on a lesion identified by PyL PET/CT scan, conventional imaging based on the Investigator's discretion (e.g., targeted MRI or CT; fluciclovine or choline PET) on the PyL-suspected lesion will be performed and sent to the central imaging core lab. The choice of the most appropriate conventional imaging modality will be at the discretion of the investigator; use of the most sensitive imaging method is encouraged, such as targeted MRI for verification of the PyL-suspected bone lesion(s).

Subjects with informative conventional imaging of the anatomical correlate to the PyL-suspected lesion(s) based on central imaging core lab review will have completed the study.

See [Section 8](#) Assessment of Efficacy.

Initiation of locoregional radiation therapy (RT) in subjects without evaluable histopathology result or informative conventional imaging of the PyL-suspected lesion(s) within 60 days following ¹⁸F-DCFPyL PET/CT

If an evaluable histopathology result for prostate cancer is not available and follow-up conventional imaging of the PyL-suspected lesion is not informative, subjects initiated on locoregional RT alone (no concomitant ADT) within 60 days following PyL PET/CT imaging will be followed every 3 months (± 7 days) for up to an additional 9 months to assess PSA response to RT alone (without concomitant ADT administered during this time). To be evaluable for PSA response, applicable subjects should undergo RT with fields and target volumes adjusted based on presence of PyL-positive prostate bed, pelvic nodal, visceral or limited osseous metastases.

A blood draw for PSA (total) will be obtained and sent to the central lab at each follow-up assessment. PSA response is defined by decline of $\geq 50\%$ from baseline PSA and must be confirmed within 4 weeks. Subjects will complete follow-up within the 9-month duration once PSA response is confirmed per the central lab.

Concomitant medications and procedures will be collected. See [Section 8](#) Assessment of Efficacy.

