8.2.3. Imaging at Biopsy (if biopsy is performed)

If a ¹⁸F-DCFPyL (PyL) PET-positive lesion is feasible for biopsy, then an image-guided biopsy should be performed on the amenable lesion. The imaging modality (e.g., CT, MRI-TRUS, US) used to guide biopsy will be collected in the eCRF. The image obtained at biopsy will be submitted for central review to confirm the anatomical location of interest correlates with the lesion identified on the PyL PET/CT.

The instruction for capturing biopsy images and directions for submitting the images to the central imaging core lab is found in the [Imaging Manual](#).

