8.3. Image Interpretation by Central Imaging Core Lab

The central imaging core lab will receive and evaluate all conventional images and PyL PET/CT scans, as applicable. Imaging data will be anonymized at the site upon image submission to the central lab and prepared for reading. PET data will be interpreted by three different independent readers in a random order at separate reading sessions. Cross sectional CT imaging from the PET/CT scans will be available for anatomic correlation. Central imaging core lab readers will be blinded to all clinical data, including PSA and histopathology (if available).

The processes for image acquisition, transmittal and interpretation are detailed in the [Imaging Manual](#) and [Imaging Review Charter](#) documents.

8.4. Histopathology from Biopsy or Surgery (if performed) of PyL-positive lesion(s) within 60 days following ¹⁸F-DCFPyL PET/CT

Within 60 days following PyL PET/CT imaging and prior to initiation of any new systemic or radiation PC therapy, if a PyL-positive lesion is identified per the site's image interpretation, tissue acquisition via surgery or image-guided biopsy should be performed if clinically feasible.

Immediately following biopsy or surgery, the specimens will be sent for local histopathological processing and analysis at the site in accordance with the study [Pathology Manual](#). Procedures and results will be recorded in the eCRF. See [Section 8.4](#) for histopathology processing and analysis at the site. If the subject's histopathology result is evaluable for prostate cancer, then no further visits are required for the subject. If histopathology is not evaluable, then see [Section 8.2.1](#) for required conventional imaging follow-up.

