Extra-pelvic (Lymph Nodes)	 Retroperitoneal (including Para/Peri-Aortic R/L and Celiac axis R/L) Supradiaphragmatic (including Supraclavicular R/L, Pre/Paratracheal R/L, Posterior Mediastinal R/L, Anterior Mediastinal R/L, Subcarinal, Paracardiac R/L, Retrocrural R/L, Thoracic Hilar R/L, Mesenteric R/L, Axillary R/L, Cervical R/L)

Statistical Analysis Plan: Protocol PyL3301

Anatomic Region	CLR Lesion Locations
	Other extra-pelvic (specify, including Inguinal/Femoral R/L)
Extra-pelvic (Bone)	 Pelvic bone R/L Skull Clavicle R/L Scapula R/L Sternum Ribcage R/L Spine (including cervical/thoracic/lumbar/sacral) Extremities (including right upper, right lower, left upper, left lower) Other bone lesion
Extra-pelvic (Visceral/soft- tissue)	 Lung/pleura Liver Other visceral/soft tissue lesion (including spleen, adrenal, mediastinum, pericardium, non-nodal retroperitoneal tissue, and other visceral/soft-tissue)

Each subject will be evaluated for the primary endpoint using a single truth standard source. If a subject has more than one source, e.g., undergoes correlative imaging and needle-guided biopsy, the pathology result from the needle biopsy will be evaluated as the truth standard. If the pathology result is unevaluable or the biopsy needle is not in a positive PyL lesion, then the results of the correlative imaging will be used as the truth standard.

Subjects with positive ¹⁸F-DCFPyL PET/CT scans per local scan interpretation (detection of disease at any location) will be followed at the Efficacy visit(s) based on their ¹⁸F-DCFPyL PET/CT finding(s) (see Section 4). If a subject has a negative ¹⁸F-DCFPyL scan by the local interpretation, then no standard of truth data will be submitted by the study site and no efficacy evaluation will be performed by the central Truth Panel readers. If the subject's ¹⁸F-DCFPyL PET/CT scan is interpreted as positive by one or more of the central readers and no standard of truth data is available for evaluation, then the subject will be considered unevaluable for the primary endpoint. Please see Section 5.1.3 for subjects with positive ¹⁸F-DCFPyL scans by local interpretation where the central reader(s) identify the scan as negative.

Subjects with positive ¹⁸F-DCFPyL PET/CT scans (by central review) will be classified as TP, FP or unevaluable as presented in Table 4.

Table 4: Primary Endpoint Assessment

Composite Truth Standard Source	Truth Standard Location Result	Central PyL Reader Location Match	Subject Outcome

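### For image-guided biopsy, the protocol lets a subject complete on evaluable local histology without waiting for the core-lab location check, yet the SAP discards that biopsy if the check fails and calls for a second truth standard the protocol does not clearly require

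*Protocol*

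**What the plan says.** **Completion after biopsy.** Protocol 4.1 says of local histopathology: "if the results are evaluable for prostate cancer, the subject will complete the study". Section 4.3.5.1 says: "Subjects with an evaluable histopathology result for prostate cancer will have completed the study". Section 8.4 says: "If the subject's histopathology result is evaluable for prostate cancer, then no further visits are required for the subject". In all three the histology is a local result, and no core-lab step is named as a condition.

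**Location check.** Protocol 8.2.3 adds: "The image obtained at biopsy will be submitted for central review to confirm the anatomical location of interest correlates" with the PyL lesion. No deadline is given, and completion is not tied to the outcome.

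**Completion after imaging.** Here Protocol 4.1 does wait for the core lab: "If the scan is deemed evaluable by the central imaging core lab, the subject will complete the study".

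**When a second standard is collected.** Table 3 footnote 6 of the protocol says that follow-up conventional imaging "is required in subjects whom evaluable histopathology for prostate cancer is not available". Under Protocol 8.1 it must fall within 60 days of the PyL scan and before locoregional or systemic treatment. PSA follow-up after RT (Protocol 8.5) is likewise reserved for subjects without evaluable histology or informative imaging.

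**What the SAP does with the biopsy.** SAP 5.1.1 deals with unusable pathology and a misplaced needle in the same way. For the latter it says that where "the biopsy needle is not in a positive PyL lesion, then the results of the correlative imaging will be used as the truth standard". Table 4 has two image-guided biopsy rows that lead to unevaluable and to another truth standard, for positive and negative pathology alike. One is for a device not in a PyL-positive lesion. The other is for sampling confirmation that is not applicable or a confirmatory image that is unevaluable. The surgical pathology rows have no device check. Under SAP 8.4, a subject with no usable standard is unevaluable.

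**The concern.** The protocol and the SAP apply different tests to the same biopsy. A site following the protocol may regard the subject as finished once the local pathologist gives an evaluable result. The SAP can later set that result aside because of where the needle was, and no passage reopens follow-up. By then the 60-day window may have closed or treatment may have begun.

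Two things are at stake. First, subjects who went through a biopsy may contribute nothing to the primary CLR although a fallback could have been obtained. Second, Protocol 10.4.2 ends enrolment and follow-up when enough positive subjects have truth-standard information for calculating the CLR. A biopsied subject satisfies item 1 of Protocol 8.1 and yet can fail SAP Table 4. A count kept on the protocol definition could therefore trigger closure with fewer evaluable subjects than planned.

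**Working it through.** **The passages side by side, for an image-guided biopsy with evaluable local histology**

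| Situation | Protocol | SAP Table 4 |
|---|---|---|
| Device confirmed in a PyL-positive lesion | Complete | Used as truth standard |
| Device not in a PyL-positive lesion | Complete, on the wording of 4.1, 4.3.5.1 and 8.4 | Unevaluable; use another standard |
| Confirmation not applicable, or image unevaluable | Complete, on the same wording | Unevaluable; use another standard |

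The last two rows do not fit together. SAP 5.1.1 itself lists unevaluable pathology and a misplaced needle as separate conditions, which suggests that evaluable histology does not already include location.

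**The plan's own figure.** Inputs from Protocol 10.1 and SAP 7.1: CLR 30%, lower limit 20%, two-sided 95% normal-approximation interval, 60% positive scans, 30% non-evaluable.

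- n = 1.96² × 0.30 × 0.70 / 0.10² = 80.67, rounded up to 81.
- 80.67 / 0.60 = 134.5 (stated as 134); 134 / 0.70 = 191.4, rounded up to 192.

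The stated 81, 134 and 192 reproduce (134 to within rounding) and are not in dispute.

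**Possible loss.** Two inputs are assumptions, because the documents give neither: biopsied share b = 20–40%, and share of checks that fail or cannot be read f = 10–25%. I also assume that none of these subjects has a second standard and that the losses come on top of the 30% allowance.

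- Lost = 81 × b × f. Low: 81 × 0.20 × 0.10 = 1.6. High: 81 × 0.40 × 0.25 = 8.1.
- Lower limit at an observed CLR of 30% = 0.30 − 1.96 × √(0.21/n):
  - n = 81: 0.2002
  - n = 79.4: 0.1992
  - n = 73: 0.1949
- Fewest true positives that clear 0.2: 25 of 81 (30.9%) or 23 of 73 (31.5%).
- Overall non-evaluable rate = 1 − 0.70 × (1 − b × f): 31.4% to 37.0%, in place of 30%.
- Scans needed = 134 / [0.70 × (1 − b × f)]: 196 to 213, in place of 192.

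With wider assumptions (b = 10–50%, f = 5–30%) the loss runs from 0.4 to 12.2 of 81.

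**The case against.** **The protocol may already leave a route to fallback imaging.** Section 4.1 also calls for imaging when biopsy or surgery of the PyL-suspected lesion was not performed, and a needle that missed the lesion arguably meets that trigger. The term evaluable is not defined for histopathology. This stands as an ambiguity, which is why the point is that the second standard is not clearly required. It does not settle the matter: the completion rules refer to a local result, and only the imaging branch names the core lab.

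**A reader might infer that subjects leave before the core lab has looked at the image.** The documents give no timing for that review, and a turnaround could sit in the Imaging Manual or Imaging Review Charter, which are not available here. What they show is that completion does not depend on the check.

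**A reader might infer that the second standard is never collected.** SAP 5.1.1 and 8.5.4 foresee subjects with both biopsy and correlative imaging. The imaging is not clearly required, but it is not barred.

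**The exclusion is deliberate.** These subjects drop out because the tissue was not shown to come from the PyL lesion. That is a defensible, conservative rule. The complaint is only that follow-up is not arranged to supply the substitute the rule calls for.

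**The plan has room for losses.** At 192 scans, 192 × 0.60 = 115 positives are expected against 81 needed, so about 34 may be lost, and failed biopsies may already be among them. Enrolment continues until enough subjects are evaluable. The imputation and tipping-point analyses of SAP 8.5.2.2 also examine unevaluable standards, but only as sensitivity analyses. This stands, with one proviso: continued enrolment protects the sample size only if the running count uses Table 4 evaluability. Protocol 4.2 and 10.4.2 and SAP section 4 speak of subjects evaluable for the primary endpoint but do not name Table 4.

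**Conclusion.** The mismatch is real and confined to image-guided biopsy. It can remove an avoidable number of subjects from the primary CLR. The number is unknown: about 2 to 8 of 81 under the assumed biopsy shares and failure rates, with a lower limit of about 19.5% at n of about 73 if the observed CLR is 30%. That figure assumes no second standard, losses additional to the 30% allowance, and no replacement by further enrolment.

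It would be tempting to say that the plan has no slack, or to carry the loss down to n = 69 and a limit of 19.2%. The documents support neither. The first ignores the allowance and the continued enrolment. The second takes 12 failures computed on 115 positives (115 × 0.40 × 0.25 = 11.5) from the 81 that remain after attrition, which mixes two bases. Nor do the documents show that early closure would occur; they only leave the counting rule open. This is a low-cost improvement that should be made, not a flaw that invalidates the primary analysis.

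**What to change.** Reconcile Protocol 4.1, 4.3.5.1, 8.4 and Table 3 footnotes 5–6 with SAP 5.1.1 and Table 4:

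- State that an image-guided biopsy completes efficacy follow-up only when histology is evaluable and the core lab has confirmed device location from the image already submitted. Otherwise treat histology as not evaluable, so that the existing fallback applies where its window is still open.
- Set a core-lab turnaround time for biopsy images.
- State how biopsies whose sampling confirmation is not applicable are handled, since they cannot meet the location condition.
- Count a biopsied subject toward the required number only once the subject is evaluable under Table 4.

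The cost is a small amendment and a turnaround commitment for images already being sent. A few subjects stay on study longer and have the follow-up imaging already specified. The remedy is partial: with a late biopsy, or where treatment has already begun, there may still be no fallback.
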